7.4.4 Categorical outcomes

Binary outcomes will be analysed with Fisher mid-P tests and Newcombe hybrid score confidence intervals for the difference between probabilities.

Ordered categorical outcomes will be analysed with score tests for effect in a proportional odds model (the Wilcoxon-Mann-Whitney test).

7.4.5 Handling of missing data

Due to a short interval of observation in the CMT trial, only 48 hours after test drug administration, we expect a low level of missing data in this trial.

For categorical outcomes and continuous outcomes measured at one or two timepoints, a complete case analysis will be the primary analysis. In addition, sensitivity analyses will be

performed for the primary outcome, where missing data will be imputed according to the following scenarios:

1. Best-case outcome in the oxytocin group and worst-case outcome in the carbetocin group.
2. Worst-case outcome in the oxytocin group and best-case outcome in the carbetocin group.

Best case outcome = group mean + 2SD

Worst case outcome = group mean - 2SD, levels below 0 are set to 0.

3. Group-specific mean values

Similar sensitivity analyses for missing data will be performed for other continuous and categorical secondary end points, if the proportion of missing outcome values is greater than 10%. Best and worst case for categorical variables will be the lowest or highest possible score according to each variable. For the binary variable occurrence of arrhythmia, for instance, best case score = 0 (no episodes of arrhythmia) and worst case score = 1 (one/more episodes of arrhythmia).

Continuous variables measured at more than two time points will be analysed with linear mixed models (Section 7.4.2), which automatically handle missing data under the missing at random assumption.

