1.0 INTRODUCTION

Adequate uterus contraction after delivery of the baby is necessary to avoid excessive bleeding. Prophylactic administration of an oxytocin receptor agonist is first line practice. Intravenous injection of oxytocin has been the standard procedure, but serious cardiovascular adverse events have been reported. Lowering the dose or administering the drug as a 5-minute infusion may increase safety.

Carbetocin, a synthetic oxytocin receptor agonist, has significantly longer half-life, and may reduce blood loss compared with oxytocin. The hemodynamic vasodilatory effects are comparable to oxytocin(1), but potential differences in adverse effects on myocardium are not well described yet.

Carbetocin has been in clinical use in EU since 2007, and the efficacy is documented in several RCTs. In the proposed study, carbetocin will be used within then conditions of the marketing authorization. Oxytocin is the first line treatment and prophylaxis in Norway and most countries in the world.

According to recently published guidelines from EU drug authorities (EMA), oxytocin should be given as a slow 5-minute infusion in order to avoid hypotension. This has so far not been implemented in Norway. The pre-clinical and clinical experience of the two drugs are summarized in the Summaries of Product Characteristics.

Pregnancy and delivery is a natural process, but for many women this period is stressful and not without risks of morbidity, and even mortality. Circulatory adverse events leading to death have been reported after intravenous injection of oxytocin(2). Some studies indicate that oxytocin may lead to dose dependant ischemic ECG changes(3, 4), prolongation of QT time and liberation of biomarkers of myocardial cell death(3).

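### The missing-data scenarios for troponin I call a high value the best case, so the two extreme runs carry each other's labels; filling in group means also understates the standard error of the linear model

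*SAP*

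**What the plan says.** For outcomes measured at one or two time points, SAP 7.4.5 makes complete-case analysis primary. It adds sensitivity analyses "performed for the primary outcome, where missing data will be imputed according to the following scenarios":

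- Scenario 1: "Best-case outcome in the oxytocin group and worst-case outcome in the carbetocin group". Scenario 2 is its mirror image.
- Definitions: "Best case outcome = group mean + 2SD" and "Worst case outcome = group mean - 2SD, levels below 0 are set to 0".
- Scenario 3: "Group-specific mean values".

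Similar analyses follow for secondary endpoints with more than 10% of values missing. Categorical endpoints use the extreme scores, and the worked example is arrhythmia: "best case score = 0 (no episodes of arrhythmia) and worst case score = 1 (one/more episodes of arrhythmia".

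Three other places set the context.

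- SAP 1.0 says oxytocin may cause "prolongation of QT time and liberation of biomarkers of myocardial cell death". It presents lower cardiotoxicity of carbetocin as the result that could change practice.
- SAP 6.1.2 has troponin I measured twice in CMT2, at baseline and at 6–10 h.
- SAP 7.4.2 regresses the follow-up value on arm and baseline. It switches to median regression with bootstrap standard errors if skewness is marked.

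**The concern.** A best-case/worst-case analysis tests whether a conclusion survives the assumption least favourable to it, so the label tells the reader which run is the hard test. Here the label attached to a high troponin I value is the favourable one. If oxytocin shows more release, as in the pilot, the run called best for oxytocin and worst for carbetocin is the easiest test of that result. The run that truly challenges it carries the label that suggests the opposite.

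Two gaps go with this. The rule does not say which of the two troponin I measurements is being filled in, and a filled-in baseline acts in the other direction. The rule is also extended to other continuous endpoints without reference to which direction is harmful.

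Scenario 3 raises a separate problem. Group means treated as observed data add subjects without adding variation, so the linear model reports too small a standard error.

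**Working it through.** **1. Direction, from the text.** Put side by side:

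| Outcome | Harmful direction | Best case in SAP 7.4.5 | Worst case in SAP 7.4.5 |
|---|---|---|---|
| Arrhythmia | 1 (event) | 0 | 1 |
| Troponin I at 6–10 h | high | mean + 2SD | mean − 2SD, not below 0 |

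The arrhythmia row puts absence of harm under best. The troponin I row puts harm there.

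**2. Inputs, checked against the plan's own figure.** SAP 7.1.2 gives a change at 10 h of 1.78 (SD 4.48) ng/L for oxytocin and 0.41 (SD 0.79) for carbetocin, a difference of 1.37. With 89 per arm, SE = √((4.48² + 0.79²)/89) = 0.482 and 1.37/0.482 = 2.84. The noncentral t with Satterthwaite df (93.5) gives power 0.803; 88 per arm gives 0.798. The planned 178 is reproduced.

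**3. Hand calculation on the change scale.** Let a share f of each arm be missing (assumed equal). Without the zero floor, the difference becomes 1.37 ± f × (2 × 4.48 + 2 × 0.79) = 1.37 ± 10.54f. With the floor applied to changes, carbetocin's low value is 0 (since 0.41 − 1.58 < 0) and so is oxytocin's (1.78 − 8.96 < 0). The shifts are then +f × (8.96 + 0.41) = +9.37f and −f × (1.78 + 1.58) = −3.36f.

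| f | Scenario 1, no floor | Scenario 2, no floor | Scenario 1, floor | Scenario 2, floor |
|---|---|---|---|---|
| 5% | 1.90 | 0.84 | 1.84 | 1.20 |
| 10% | 2.42 | 0.32 | 2.31 | 1.03 |

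Scenario 1, best for oxytocin by its label, makes oxytocin look worse.

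**4. Simulation on the level scale with the SAP 7.4.2 model.** There were 120 per arm, values missing completely at random, and 3,000 trials. Change was gamma with the pilot means and SDs. The documents give no baseline mean, so 1, 3 and 6 ng/L with CV 50% were assumed. The table shows the shift in the oxytocin-minus-carbetocin difference from complete case, in ng/L.

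| Value missing | Scenario | 5% missing | 10% missing |
|---|---|---|---|
| Follow-up | 1 | +0.50 / +0.62 / +0.83 | +1.01 / +1.25 / +1.66 |
| Follow-up | 2 | −0.23 / −0.41 / −0.70 | −0.46 / −0.82 / −1.40 |
| Baseline | 1 | −0.08 / −0.25 / −0.49 | −0.14 / −0.42 / −0.84 |

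With follow-up missing, the direction held in 100% of trials. With baseline missing, scenario 1 lowered the difference in 85–100%. Under median regression (400 trials, follow-up missing), scenario 1 still raised the difference in 100% of trials, but only by about 0.05 at 5% and 0.12 at 10%.

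**5. Scenario 3, linear model.** Let r be the baseline–follow-up correlation, which the documents do not give. After filling in raw follow-up means, and up to a common factor:

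- variance the model reports: (1−f) − (1−f)²r²
- true variance: 1/(1−f) − 2(1−f)r² + (1−f)²r²

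At f = 10% and r = 0.5 these are 0.6975 and 0.8636, and √(0.6975/0.8636) = 0.90. Over r = 0 to 0.9 the ratio of reported to true SE is about 0.95 at 5% missing and 0.89–0.90 at 10%.

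Null simulations (4,000 trials, normal and lognormal data, r = 0.3 to 0.9) gave ratios of 0.93–0.96 and 0.89–0.90. A nominal 5% test rejected in 5.8–6.7% and 7.0–8.6% of trials; complete case rejected in 4.2–5.8%. A further normal-data set with r = 0, 0.5 and 0.9 gave rejection of 6.3–6.5% and 7.3–9.3%.

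**6. Scenario 3, median regression.** With 100 bootstrap replications and 700–1,200 trials, rejection was 3.7–4.9% at 5% missing and 3.9–6.1% at 10%, against 3.7–4.7% for complete case. No clear inflation was seen.

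**The case against.** The strongest reply is that relabelling changes no number. The same two imputed values go to the same two arm allocations, so the pair of estimates is identical before and after the correction. The shifts above are what any ±2SD scenario would produce, so they do not measure the label error. That stands. They show the direction of each run, and how much hangs on knowing which is which. A careful reader could also work out the direction from the printed definitions; a reader relying on the labels would not.

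Second, the pilot SD of 4.48 against a mean of 1.78 suggests skewness, so median regression may well be used. There the shifts are small and scenario 3 does no visible harm. This limits the scenario 3 point to the linear model, but the label direction is the same under both.

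Third, the SAP says "we expect a low level of missing data in this trial", and the full analysis set contains only women who received study drug, so those who leave before dosing do not count as missing. The practical effect may be small.

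Fourth, at r = 0.9 the scenario 3 SE is 1.05–1.08 times the complete-case SE, so its interval can be wider than the primary one. It is still too small for the estimate it accompanies, at 0.89–0.95 of the true value.

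Finally, follow-up is the natural reading of a missing outcome, and one phrase would settle it. A blanket reversal would be wrong for uterine tone, where high is good. For that endpoint only the direction of the present rule fits: the scale ends at 10 and the rule has no upper cap.

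**Conclusion.** The point holds. For a missing follow-up troponin I value, SAP 7.4.5 has best and worst the wrong way round, contrary to the trial's rationale and to the section's own arrhythmia example. Each extreme run therefore points opposite to its label. The direction did not depend on the assumed baseline mean, the share missing, or the choice of linear or median regression.

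The consequence is one of interpretation. The complete-case primary analysis, the sample size and the range spanned by the two runs are untouched.

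Scenario 3 is a lesser fault and carries no decision. If the linear model is kept, it understates the SE by about 5% at 5% missing and 10% at 10%, and a nominal 5% test runs at about 6% or 8%. These sizes assume values missing completely at random in equal shares per arm. The SAP should be corrected, but no main result depends on it.

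**What to change.** Amend SAP 7.4.5 before allocation is revealed:

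- For a missing follow-up troponin I value, define worst case as group mean + 2SD and best case as group mean − 2SD, not below 0. State that scenario 1 then favours oxytocin and scenario 2 favours carbetocin.
- State that the scenarios fill in the 6–10 h value, and say separately how a missing baseline is handled.
- For any other continuous endpoint to which the rule is applied, set best and worst by that endpoint's harmful direction and keep filled-in values within the scale.
- Delete scenario 3. Multiple imputation by arm, with baseline troponin I in the imputation model and Rubin's rules, is an optional replacement. It corrects the SE but gives nearly the complete-case adjusted estimate.

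The cost is a few lines of text and one fewer sensitivity run. It needs no new data and no change to the sample size.

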2.0 DATA SOURCE

2.1 Patients

We will conduct a double blinded randomized controlled trial where healthy women undergoing C-section will receive either oxytocin or carbetocin immediately after delivery of the baby. Ratio between the groups will be 1:1.

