4.2 Statistical decision rule

The primary and all secondary outcomes will be analysed with two-sided tests and confidence intervals and a statistical significance level of 5%.

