7.1.2 CMT2 trial

Based on preliminary results of the CMT pilot trial, the largest difference in plasma troponin I concentration was found at 10 hours, with a mean±standard deviation change from baseline of 0.41 ± 0.79 ng/L in the carbetocin group versus a mean change of 1.78 ± 4.48 in the oxytocin group. The sample size calculation was based on 80% power to detect a between-group difference in change from baseline to 10 hours of 1.37, to be analysed using a two-sample T-test with adjustments for unequal variances. With a significance level of 5%, we will need to include 178 patients (89 in each treatment group) in the CMT2 trial. To adjust for loss of information from missing values and patient drop outs, 240 women will be enrolled. The drop-out rate after enrolment is expected to be low as the duration of the study is short.

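### SAP 7.4.5 reverses best and worst case for troponin I, and its own-arm ±2SD fills make the run that tests a carbetocin advantage too mild

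*SAP*

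**What the plan says.** SAP 7.4.5 makes complete-case analysis primary for outcomes measured at one or two time points, which includes CMT2 troponin I. It then plans three sensitivity fills for the primary outcome. Scenario 1 gives missing oxytocin values the best case and missing carbetocin values the worst case. Scenario 2 does the opposite. Scenario 3 uses group-specific means. For continuous outcomes the rule is "Best case outcome = group mean + 2SD", with worst case at the mean minus 2SD and negative levels set to 0. For categorical outcomes the same section says "Best and worst case for categorical variables will be the lowest or highest possible score according to each variable", and its arrhythmia example takes no event as best and an event as worst.

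SAP 7.1.2 gives the pilot changes from baseline to 10 hours as "0.41 ± 0.79 ng/L in the carbetocin group versus a mean change of 1.78 ± 4.48 in the oxytocin group". SAP 1.0 presents troponin I as a marker of cardiotoxicity and asks which drug releases more of it. SAP 7.4.2 analyses follow-up troponin I by linear regression on arm and baseline, and switches to median regression if skewness is marked.

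**The concern.** There are two defects in the one rule.

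- **Direction.** More troponin release is worse, yet the high value is called best. Someone who looks for the run hardest on carbetocin would go to Scenario 1, which in fact widens the gap in carbetocin's favour.
- **Size.** An extreme-case run is meant to challenge the assumption that missing women resemble the observed women of their own arm. Filling from each arm's own mean and SD builds that assumption back in. With a pilot variance ratio of 4.48²/0.79² ≈ 32, a missing carbetocin value is filled far below the oxytocin upper range. The categorical rule in the same section has no such problem, because it uses one bound for both arms.

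At stake is whether a finding that oxytocin releases more troponin can fairly be called robust to missing data.

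**Working it through.** All differences are oxytocin minus carbetocin, in ng/L. A positive value means a carbetocin advantage.

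**Inputs.** Pilot changes are from SAP 7.1.2. I take 120 per arm from 240 women and "Ratio between the groups will be 1:1". The missing fraction and the troponin level are not in the documents and are assumed.

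**1. The plan's own figure.** The target is "80% power to detect a between-group difference in change from baseline to 10 hours of 1.37" by a "two-sample T-test with adjustments for unequal variances". The root-mean-square SD is √((0.79² + 4.48²)/2) = 3.217. Two-sided Welch power at 5% is 79.8% with 88 per arm and 80.3% with 89, so 178 is reproduced.

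**2. Own-arm fills, change scale.** The floor is applied as if baseline were 0, for illustration.
- Carbetocin: high 0.41 + 2×0.79 = 1.99; low 0.41 − 1.58 = −1.17, floored to 0.
- Oxytocin: high 1.78 + 2×4.48 = 10.74; low 1.78 − 8.96 = −7.18, floored to 0.

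**3. Effect at missing fraction p.** Filled difference = (1 − p)×1.37 + p×(oxytocin fill − carbetocin fill). At p = 0.10:
- Scenario 1 (oxytocin high, carbetocin low): 1.233 + 0.1×10.74 = 2.31, a shift of +0.94.
- Scenario 2 (oxytocin low, carbetocin high): 1.233 − 0.1×1.99 = 1.03, a shift of −0.34.

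Each arm's variance is (1 − p)s² + p(1 − p)(fill − mean)². In Scenario 2 this gives 0.786 and 18.35, SE = √(19.14/120) = 0.399, and 95% CI 0.25 to 1.82.

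**4. One common pair of fills.** For all women combined the mean is (0.41 + 1.78)/2 = 1.095 and the SD is √(3.217² + 0.685²) = 3.289. The high fill is 1.095 + 6.578 = 7.67 and the low fill is floored to 0. At p = 0.10, Scenario 2 gives 1.233 − 0.767 = 0.47 (CI −0.40 to 1.34) and Scenario 1 gives 1.233 + 0.767 = 2.00. The fill differences are now +7.67 and −7.67, equal and opposite around zero.

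**5. Role of the floor.** Without it, the own-arm fill differences are 10.74 + 1.17 = 11.91 and −7.18 − 1.99 = −9.17. Each lies 2×(0.79 + 4.48) = 10.54 from 1.37, so the two runs shift the result equally. With the floor the distances are 9.37 and 3.36. If level SDs equalled the change SDs, the oxytocin floor would stop binding at a baseline of 8.96 − 1.78 = 7.18 ng/L.

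**6. Level scale, planned linear model.** I simulated 120 per arm with lognormal baseline, normal carbetocin changes, normal or right-skewed oxytocin changes, and values missing completely at random. At baseline 2.5 (SD 1.5) the own-arm high fills are about 6.2 for carbetocin and 12.4 to 13.7 for oxytocin. The results for the carbetocin-high, oxytocin-low run are:

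| Assumed baseline (SD) | Missing per arm | Own-arm fill | Common fill |
|---|---|---|---|
| 2.5 (1.5) | 2% | about 1.24 | about 1.17 |
| 2.5 (1.5) | 5% | about 0.98 | about 0.77 |
| 2.5 (1.5) | 10% | about 0.6 | about 0.2 |
| 8 (2) | 10% | about 0 | about −0.3 |

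At 2.5 (1.5) and 10% missing, the CI stays above 0 in about 23–29% of trials with own-arm fills and 0–2% with common fills. At 8 (2) it does so in at most 2% under either rule.

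**7. Median analysis.** Filling 10% of simulated carbetocin changes at 1.99 or at 10.74 gives the same median, 0.52.

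**The case against.** Much of the case on the other side stands.

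- The documents give no troponin level. If levels are high enough for the floor not to bind, own-arm fills shift both runs equally. Near 8 ng/L, with 10% missing, Scenario 2 removes the carbetocin advantage under either rule.
- SAP 7.4.2 expects skewness and may move to median regression, where the size of the fill hardly matters.
- SAP 7.4.5 expects few missing values, and women who did not receive study drug are outside the full analysis set (SAP 5.2).
- The pilot SDs describe changes in a 40-woman study. CMT2's own SDs would be used.
- Own-arm fills are not toothless: at 10% missing and the low baseline they already cost significance in most simulated trials.
- In the normal-change variant at the low baseline, some oxytocin levels would be negative. The right-skewed variant gives nearly the same result.

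One objection fails. It says that a common fill is merely lopsided the other way. Its shifts are indeed unequal (+0.63 and −0.90 at 10% on the change scale), but only because the observed difference is not zero. The fills themselves are equal and opposite, as extreme bounds should be.

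A reader might also infer that unequal SDs alone tilt the range towards carbetocin, or that the run labelled worst for carbetocin is merely too weak. The documents support neither. The tilt needs the floor, and the run with that label points the wrong way.

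**Conclusion.** The labels are reversed for troponin I, on the SAP's own account of what the marker means and against its own arrhythmia example. Both runs are planned, so correcting the labels leaves the two numbers as they are and changes only which one is read as adverse to carbetocin.

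The carbetocin-high, oxytocin-low run is milder than under a common pair of fills at every baseline tried. Where the floor binds, the range is also lopsided in carbetocin's favour. The size rests on assumed levels and missing fractions: a gap of about 0.4 ng/L at baseline 2.5 (SD 1.5) with 10% missing, about 0.2 at 5%, and under 0.1 at 2%. It applies to the linear model.

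It would go too far to conclude that a carbetocin advantage will be wrongly declared robust. That can happen at low levels with appreciable missing data, but the documents do not show that those conditions will arise. The primary analysis is untouched.

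**What to change.** In SAP 7.4.5:

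1. Define best case as the low and worst case as the high troponin I value.
2. State that follow-up levels, not changes, are filled.
3. For Scenarios 1 and 2 use one pair of fills in both arms: the mean + 2SD and the mean − 2SD (floor 0) of follow-up troponin I in all women with a value, arms combined.
4. Apply the same common-bound rule to continuous secondary outcomes, and state for each whether high or low is the favourable direction.

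The cost is a few sentences and no new data. The downside is that the sensitivity range becomes somewhat less favourable to a claim of robustness.

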7.4.6 Statistical software

StataSE version 16 (StataCorp LLC, College Station, TX) will be used for all statistical analyses, except analyses of categorical outcomes, which will be done with MATLAB version R2019b (MathWorks, Inc.).

